### **5.4.1.3 Exploratory Efficacy Endpoints**

#### **5.4.1.3.1 Immune-related RECIST**

RECIST 1.1 will be adapted to account for the unique tumor response characteristics seen following the treatment of pembrolizumab. Immunotherapeutic agents such as pembrolizumab may produce antitumor effects by potentiating endogenous cancer-specific immune responses. The response patterns seen with such an approach may extend beyond the typical time course of responses seen with cytotoxic agents, and participants may manifest a clinical response after an initial increase in tumor burden or even the appearance of new lesions. Standard RECIST 1.1 may, therefore, not provide an accurate response assessment of immunotherapeutic agents such as pembrolizumab.

Based on an analysis of participants with melanoma enrolled in the KEYNOTE-001 trial, 7% of evaluable participants experienced delayed or early tumor pseudo-progression. Of note, participants who had PD by RECIST 1.1, but not by irRECIST, had longer OS than participants with PD by both criteria. Additionally, the data suggest that RECIST 1.1 may underestimate the benefit of pembrolizumab in approximately 15% of participants. These findings support the need to apply a modification to RECIST 1.1 that takes into account the unique patterns of atypical response in immunotherapy and enables treatment beyond initial radiographic progression.

The irRECIST assessment is based on RECIST 1.1 and is adapted to account for the unique tumor response seen with immunotherapeutics as described in Nishino et al., CCR 2013 [Nishino, M., et al 2013]. The assessment of unidimensional target lesions and response categories per irRECIST are identical to RECIST 1.1. However, MSD has implemented an adaptation related to new lesions, non-target lesions, and tumor burden assessment in order to confirm radiographic progression. Immune-related RECIST will be used by local site investigators to assess tumor response and progression, and to make treatment decisions, as well as used by the central imaging vendor in support of the PFS, ORR, DCR, and DOR endpoint. For further information on irRECIST, see Section 9.2.1.6.

#### **5.4.1.4 Rationale for Patient-reported Outcomes**

Changes in health-related quality of life (HRQoL) measured using patient-reported outcome (PRO) assessments can provide important information on clinical benefit and are accepted clinical endpoints by health authorities. Participants will provide information regarding their HRQoL using the EORTC QLQ-C30 PRO instrument. Health utilities will be evaluated

using the EuroQol-5D (EQ-5D) PRO instrument. These PRO assessments are not pure efficacy or safety endpoints because they are affected by both disease progression and treatment tolerability.

### **EORTC QLQ-C30**

EORTC QLQ-C30 is the most widely used cancer-specific health-related quality of life (QoL) instrument, which contains 30 items and measures 5 functional dimensions (physical, role, emotional, cognitive, and social), 3 symptom items (fatigue, nausea/vomiting, and pain), 6 single items (dyspnea, sleep disturbance, appetite loss, constipation, diarrhea, and financial impact), and a global health and QoL scale [Aaronson, N. K., et al 1993]. The EORTC QLQ-C30 is a psychometrically and clinically validated instrument appropriate for assessing QoL in oncology trials [Aaronson, N. K., et al 1993].

### **EuroQol EQ-5D**

The EuroQol-5D is a standardized instrument for use as a measure of health outcome and will provide data to develop health utilities for use in health economic analyses [Aaronson, N. K., et al 1993]. The 5 health state dimensions in the EQ-5D include the following: mobility, self-care, usual activities, pain/discomfort, and anxiety/depression. Each dimension is rated on a 5 point scale from 1 (no problem) to 5 (unable to/extreme problems). The EQ-5D also includes a graded (0 to 100) vertical visual analog scale on which the participant rates his or her general state of health at the time of the assessment. This instrument has been used extensively in cancer studies and published results from these studies support its validity and reliability [Pickard, A. S., et al 2007].

#### **5.4.1.5 Rationale for Safety Endpoints**

Safety parameters commonly used for evaluating investigational systemic anticancer treatments are included as safety endpoints including, but not limited to, the incidence of, causality, and outcome of AEs/SAEs, and changes in vital signs and laboratory values. Adverse events will be assessed as defined by CTCAE, Version 4.0.

#### **5.4.1.6 Pharmacokinetic Endpoints**

Pharmacokinetics of pembrolizumab will be explored per existing modeling analysis plan (MAP).

#### **5.4.1.7 Planned Exploratory Biomarker Research**

Cancer immunotherapies represent an important and novel class of anti-tumor agents. However, the mechanism of action of these exciting new therapies is not completely understood and much remains to be learned regarding how best to leverage these new drugs in treating patients. Thus, to aid future patients, it is important to investigate the determinants of response or resistance to cancer immunotherapy, as well as determinants of AEs in the course of our clinical trials. These efforts will identify novel predictive/PD biomarkers and generate information that will better guide single-agent and combination therapy with

immune-oncology drugs. To identify novel biomarkers, biospecimens (ie, blood components, tumor material, etc.) will be collected to support analyses of cellular components (eg, protein, DNA, RNA, metabolites) and other circulating molecules. Investigations may include but are not limited to:

#### **5.4.1.7.1 Germline Genetic Analyses**

Germline (blood) genetic analyses (eg, single nucleotide polymorphism [SNP] analyses, whole exome sequencing, whole genome sequencing): This research will evaluate whether genetic variation within a clinical trial population correlates with response to the treatment(s) under evaluation. If genetic variation is found to predict efficacy or AEs, the data might inform optimal use of therapies in the patient population. Furthermore, it is important to evaluate germline DNA variation across the genome in order to interpret tumor-specific DNA mutations.

#### **5.4.1.7.2 Tumor Genetic Analyses**

Genetic (DNA) analyses from tumor: The application of new technologies, such as next generation sequencing, has provided scientists the opportunity to identify tumor-specific DNA changes (ie, mutations, methylation status, microsatellite instability). Key molecular changes of interest to immune-oncology drug development include the mutational burden of tumors and the clonality of T-cells in the tumor microenvironment. Increased mutational burden (sometimes referred to as a "hyper-mutated" state) may generate neo-antigen presentation in the tumor microenvironment. To conduct this type of research, it is important to identify tumor-specific mutations that occur across all genes in the tumor genome. Thus, genome-wide approaches may be used for this effort. Note that in order to understand tumor-specific mutations it is necessary to compare the tumor genome with the germline genome. Microsatellite instability may also be evaluated as this is an important biomarker for some cancers (ie, colorectal cancer).

#### **5.4.1.7.3 Tumor and Blood RNA Analyses**

Both genome-wide and targeted messenger RNA (mRNA) expression profiling and sequencing in tumor tissue and in blood may be performed to define gene signatures that correlate to a clinical response to treatment with pembrolizumab or other immunotherapies. Pembrolizumab induces a response in tumors that likely reflects an inflamed/immune phenotype. Specific immune-related gene sets (ie, those capturing interferon-gamma transcriptional pathways) may be evaluated and new signatures may be identified. Individual genes related to the immune system may also be evaluated (eg, IL-10). MicroRNA profiling may also be pursued.

#### **5.4.1.7.4 Proteomic Biomarkers and IHC**

Proteomics and IHC using blood or tumor: Tumor and blood samples from this trial may undergo proteomic analyses (eg, PD-L1 IHC). PD-L1 protein level in tumor sections, assessed by IHC, has been shown to correlate with response to pembrolizumab in patients

with non-small cell lung cancer (NSCLC), and an in vitro diagnostic (IVD) device has been developed for use with pembrolizumab in NSCLC. Preliminary data indicates that this association may also be true in additional cancer types (ie, triple negative breast cancer, head and neck, and gastric). Additional tumor or blood-derived proteins may also correlate with response to pembrolizumab. Therefore, tumor tissue may be participant to proteomic analyses using a variety of platforms that could include but are not limited to immunoassays and liquid chromatography/mass spectrometry. This approach could identify novel protein biomarkers that could aid in patient selection for pembrolizumab (MK-3475) therapy.

#### **5.4.1.7.5 Other Blood Derived Biomarkers**

In addition to expression on the tumor tissue, PD-L1 and other tumor-derived proteins can be shed from tumors and released into the blood. Assays such as enzyme-linked immunosorbent (ELISA) measure such proteins in serum. Correlation of expression with response to pembrolizumab therapy may identify new approaches for predictive biomarkers in blood, representing a major advance from today's reliance on assessing tumor biomarkers. This research would serve to develop such assays for future clinical use.

#### **5.4.1.8 Future Biomedical Research**

The Sponsor will conduct Future Biomedical Research on specimens consented for future biomedical research during this clinical trial. This research may include genetic analyses (DNA), gene expression profiling (RNA), proteomics, metabolomics (serum, plasma) and/or the measurement of other analytes, depending on which specimens are consented for future biomedical research.

Such research is for biomarker testing to address emergent questions not described elsewhere in the protocol (as part of the main trial) and will only be conducted on specimens from appropriately consented participants. The objective of collecting/retaining specimens for Future Biomedical Research is to explore and identify biomarkers that inform the scientific understanding of diseases and/or their therapeutic treatments. The overarching goal is to use such information to develop safer, more effective drugs/vaccines, and/or to ensure that participants receive the correct dose of the correct drug/vaccine at the correct time. The details of future biomedical research are presented in Appendix 6.

### **5.5 Justification for Dose**

#### **5.5.1 Rationale for Pembrolizumab Dose**

The planned dose of pembrolizumab for this trial is 200 mg every 3 weeks (Q3W). Based on the totality of data generated in the KEYTRUDA® development program, 200 mg Q3W is the appropriate dose of pembrolizumab across all indications and regardless of tumor type. As outlined below, this dose is justified by:

- Clinical data from eight randomized studies demonstrating flat dose- and exposure-efficacy relationships from 2 mg/kg Q3W to 10 mg/kg every two weeks (Q2W)

- Clinical data showing meaningful improvement in benefit-risk including overall survival at 200 mg Q3W across multiple indications
- Pharmacology data showing full target saturation in both systemic circulation (inferred from pharmacokinetic [PK] data) and tumor (inferred from physiologically based pharmacokinetic [PBPK] analysis) at 200 mg Q3W

Among the eight randomized dose-comparison studies, a total of 2262 subjects were enrolled with melanoma and non-small cell lung cancer (NSCLC), covering different disease settings (treatment naïve, previously treated, PD-L1 enriched and all-comers) and different treatment settings (monotherapy and in combination with chemotherapy). Five studies compared 2 mg/kg Q3W versus 10 mg/kg Q3W (KN001 B2, KN001 D, KN002, KN010 and KN021), and three studies compared 10 mg/kg Q3W versus 10 mg/kg Q2W (KN001 B3, KN001 F2 and KN006). All of these studies demonstrated flat dose- and exposure-response relationships across the doses studied representing an approximate 5 to 7.5 fold difference in exposure. The 2 mg/kg (or 200 mg fixed-dose) Q3W provided similar responses to the highest doses studied. Subsequently, flat dose-/exposure-response relationships were also observed in other tumor types including head and neck cancer, bladder cancer, gastric cancer and classical Hodgkin Lymphoma, confirming 200 mg Q3W as the appropriate dose independent of the tumor type. These findings are consistent with the mechanism of action of pembrolizumab, which acts by interaction with immune cells, and not via direct binding to cancer cells.

Additionally, pharmacology data clearly show target saturation at 200 mg Q3W. First, PK data in KN001 evaluating target-mediated drug disposition (TMDD) conclusively demonstrated saturation of PD-1 in systemic circulation at doses much lower than 200 mg Q3W. Secondly, a PBPK analysis was conducted to predict tumor PD-1 saturation over a wide range of tumor penetration and PD-1 expression. This evaluation concluded that pembrolizumab at 200 mg Q3W achieves full PD-1 saturation in both blood and tumor.

Finally, population PK analysis of pembrolizumab, which characterized the influence of body weight and other subject covariates on exposure, has shown that the fixed-dosing provides similar control of PK variability as weight based dosing, with considerable overlap in the distribution of exposures from the 200 mg Q3W fixed dose and 2 mg/kg Q3W dose. Supported by these PK characteristics, and given that fixed-dose has advantages of reduced dosing complexity and reduced potential of dosing errors, the 200 mg Q3W fixed-dose was selected for evaluation across all pembrolizumab protocols.

## **6. Study Population**

Male/Female participants with R/M cSCC or LA unresectable cSCC  $\geq$  18 years of age will be enrolled in this trial.

Prospective approval of protocol deviations to recruitment and enrollment criteria, also known as protocol waivers or exemptions, is not permitted.

## 6.1 Inclusion Criteria

Participants are eligible to be included in the study only if all of the following criteria apply:

### Type of Participant and Disease Characteristics

1. R/M disease cohort only – All participants must have cSCC that is either metastatic, defined as disseminated disease, and/or unresectable disease that is not curable by surgery or radiation.
2. Participants must have histologically confirmed cSCC as the primary site of malignancy (metastatic skin involvement from another primary cancer or from an unknown primary cancer is not permitted).

Note: Participants for whom the primary site of squamous cell carcinoma was anogenital area (penis, scrotum, vulva, perianal region) are not eligible. Participants with tumors arising on cutaneous non-glabrous (hairbearing) lip with extension onto vermillion (dry red lip) may be eligible after communication and approval from the clinical director. Participants for whom the primary site is the nose may be eligible after communication and approval from the clinical director if the primary site is skin, not nasal mucosa with outward extension to skin.

Note: Participants who have squamous cell parotid metastases and have been treated previously for cSCC are permitted.

3. LA disease cohort only – Participants must be ineligible for surgical resection.  
Contraindications for surgical resection:
  - cSCC that has recurred in the same location after 2 or more surgical procedures and not amenable to curative resection.
  - cSCC with significant local invasion that prevents total resection.
  - cSCC in anatomically challenging locations for which surgery is not feasible and may result in severe dysfunction and disfigurement (eg, nose, ear, eye resections, or limb amputation).
4. LA disease cohort only – Participants who received prior radiation therapy(RT) to index site or must be deemed to be not eligible for RT.

Contraindications (Ineligibility) for RT:

- cSCC in anatomically challenging locations for which RT would be associated with unacceptable toxicity risk.
- Patients who have previously received maximum recommended cumulative dose of RT at the index site for cSCC.

5. LA disease cohort only – Participants who received prior systemic therapy for curative intent are eligible regardless of regimen.
6. R/M disease cohort only – Participants must have metastatic disease, defined as disseminated disease distant to the initial/primary site of diagnosis, and/or must have locally recurrent disease that has been previously treated (with either surgery or radiotherapy) and is not curable by either surgery or radiotherapy.

Note: There is no requirement for prior chemotherapy and/or biological systemic treatment for incurably recurrent and/or metastatic disease

Note: There is no limit to the number of prior systemic therapies that a participant may have received in order to meet eligibility for this trial.

7. Participants must have measurable disease based on RECIST 1.1 as assessed by the central imaging vendor. Lesions situated in a previously irradiated area are considered measurable if progression has been demonstrated in such lesions.

Note: The site investigator must confirm the participant has measurable disease per RECIST 1.1 prior to submitting to the central vendor.

8. Participants must have an Eastern Cooperative Oncology Group (ECOG) performance status of 0 to 1 within 10 days prior to the start of treatment.
9. Participants must have adequate organ function as defined in the following table (Table 3). Specimens must be collected within 10 days prior to the start of treatment.

Table 3 Adequate Organ Function Laboratory Values

System	Laboratory Value
Hematological	
Absolute neutrophil count (ANC)	≥ 1500 cells/μL without granulocyte colony-stimulating factor (G-CSF) support within 2 weeks prior to the first dose of study treatment
Platelets	≥100 000/μL
Hemoglobin	≥9 g/dL or ≥5.6 mmol/L. Participants are eligible if levels are reached after blood transfusion.
Renal	
a Measured or calculated creatinine clearance (GFR can also be used in place of creatinine or CrCl)	≤1.5 × ULN OR ≥45 mL/min for participants with creatinine levels >1.5 × institutional ULN
Hepatic	
b Total bilirubin	≤1.5 × ULN OR direct bilirubin ≤ ULN for participants with total bilirubin levels >1.5 × ULN
AST (SGOT) and ALT (SGPT)	≤2.5 × ULN (≤5 x ULN for participants with liver metastases)
Coagulation	
c International normalized ratio (INR) OR PT and aPTT	≤1.5 × ULN unless participant is receiving anticoagulant therapy as long as prothrombin time (PT) or activated partial thromboplastin time (aPTT) is within therapeutic range of intended use of anticoagulants
a Creatinine clearance should be calculated per institutional standard. b For participants with Gilbert's disease, total bilirubin may be >1.5 × ULN; however, direct bilirubin must be normal. c Partial thromboplastin time (PTT) may be performed if the local laboratory is unable to perform aPTT. ALT (SGPT) = alanine aminotransferase (serum glutamic pyruvic transaminase); AST (SGOT) = aspartate aminotransferase (serum glutamic oxaloacetic transaminase); CrCl = creatinine clearance; GFR = glomerular filtration rate; ULN = upper limit of normal.	

10. Participants must have a tissue sample adequate for PD-L1 testing as determined by central laboratory testing prior to trial allocation. This tissue sample may be obtained from either a newly obtained core or excisional biopsy, or a prior archival tissue specimen.

Note: Participants from whom PD-L1 testing cannot be performed due to infeasibility of testing of the tissue sample will not be eligible.

Note: Submit an evaluable sample for analysis. If submitting unstained cut slides, freshly cut slides should be submitted to the testing laboratory within 14 days from when the slides are cut. See Section 9.7 – Pharmacodynamics for an explanation.

11. Participants must have a life expectancy of greater than 3 months.

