### Locally Advanced (LA) high-risk cSCC

LA high-risk cSCC is defined as cSCC that has high-risk features, including regional nodal disease, and has no distant metastasis. High-risk features of cSCC defined per National Comprehensive Cancer Network (NCCN) Guidelines for Squamous Cell Skin Cancer [National Comprehensive Cancer Network 2017] include depth of invasion, histologic features, anatomical location, horizontal size, perineural involvement, tumor recurrence, incomplete excision, multiple tumors, patient characteristics, and genetic/molecular markers [Burton, K. A., et al 2016] [National Comprehensive Cancer Network 2017]. The majority of patients with cSCC are successfully treated with surgical resection of the primary site. Patients with high-risk features are at risk for local recurrence and regional metastasis and these patients have significantly worse outcomes compared to those cured by initial surgery.

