### 5.2 Number of Participants

Up to approximately 100 study participants with incurably recurrent and/or metastatic cSCC and 50 participants with LA unresectable cSCC will be allocated.

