### Medical Conditions

1. Participant has cSCC that can be cured with surgical resection, radiotherapy, or with a combination of surgery and radiotherapy.
2. Participant has any other histologic type of skin cancer other than invasive squamous cell carcinoma as the primary disease under study, eg, basal cell carcinoma that has not been definitively treated with surgery or radiation, Bowen's disease, MCC, melanoma.
3. Participants with any prior allogeneic solid organ or bone marrow transplantations are excluded.

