### **7.3 Method of Treatment Assignment**

Treatment allocation will occur centrally using an interactive voice response system/integrated web response system (IVRS/IWRS).

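### Does the plan need a rule for incurable local recurrences that fit both the R/M and the LA cohort?

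*Combined protocol and SAP*

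**What the plan says.** **R/M entry (Section 6.1, criteria 1 and 6).** Both criteria join their alternatives with and/or, so metastasis is not required. Criterion 1 accepts metastatic disease "and/or unresectable disease that is not curable by surgery or radiation". Under criterion 6 the participant must have distant disease and/or "must have locally recurrent disease that has been previously treated (with either surgery or radiotherapy) and is not curable by either surgery or radiotherapy".

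**LA entry (Section 6.1, criteria 3 and 4).** Surgery must be ruled out, and one listed ground is "cSCC that has recurred in the same location after 2 or more surgical procedures and not amenable to curative resection". For radiotherapy the wording is "Participants who received prior radiation therapy(RT) to index site or must be deemed to be not eligible for RT".

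**Text that might separate the cohorts.** Exclusion criterion 1 in Section 6.2 removes anyone for whom "Participant has cSCC that can be cured with surgical resection, radiotherapy, or with a combination of surgery and radiotherapy", but it applies to both cohorts. The background in Section 3.2.1 says "LA high-risk cSCC is defined as cSCC that has high-risk features, including regional nodal disease, and has no distant metastasis". That paragraph also lists tumor recurrence as a high-risk feature.

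**Allocation and analysis.** Section 5.2 sets the sizes: "Up to approximately 100 study participants with incurably recurrent and/or metastatic cSCC and 50 participants with LA unresectable cSCC will be allocated". Section 7.3 says "Treatment allocation will occur centrally using an interactive voice response system/integrated web response system (IVRS/IWRS"), and Section 9.1.7 limits each participant to one treatment number. Sections 10.6.1 and 10.6.2 analyse efficacy and safety by cohort. Section 10.10 lists age, sex, race and region as subgroups for ORR. Section 10 sends changes to exploratory analyses to a supplemental SAP, which is not among the documents.

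**The concern.** The primary result is one ORR per cohort, so a reader needs to know whom each describes. An incurable same-site recurrence after two or more operations, in a participant already irradiated there, appears to qualify for both. Without an assignment rule, sites could place similar patients differently, and part of the R/M cohort could resemble the LA cohort.

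A second worry is separate. Even if nobody was eligible for both, the R/M cohort mixes distant metastatic disease with purely local recurrence, and Section 10.10 plans no split. If the two respond differently, the pooled R/M ORR describes neither well. What is at stake is interpretation: no biased measurement or wrong calculation is alleged.

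**Working it through.** **1. Do the criteria overlap?** Take a participant without distant metastasis whose tumor has recurred at the same site after two operations and prior radiotherapy there, and is incurable by either.

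| Requirement | Met? |
|---|---|
| R/M criterion 1: unresectable and incurable | yes |
| R/M criterion 6: previously treated, incurable local recurrence | yes |
| LA criterion 3, first ground | yes |
| LA criterion 4: prior radiotherapy to the index site | yes |
| Exclusion 1: curable disease | not triggered |

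The overlap exists on the wording. Sections 5.1, 5.2, 7.3, 7.3.1 and 9.1.7 give no precedence rule.

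**2. When could it arise?** The Document History shows that the LA cohort was added by Amendment 03 (25-SEP-2018). The study began under the protocol of 21-APR-2017. The R/M schedule in Section 2.1 provides for complete responses reached before Amendment 03, and the LA schedule in Section 2.2 does not. Participants allocated before the amendment had only one cohort to enter. Double eligibility is confined to R/M participants allocated afterwards. The documents do not give their number, which may be zero.

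**3. Are the planning figures right?** Find the smallest responder count whose two-sided exact 95% lower bound exceeds the target in Section 10.9.1, then take the binomial tail.

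- R/M: 23 of 100 (lower bound 15.17%). P(X ≥ 23 | 100, 0.30) = 0.952, as in Table 13.
- LA: 17 of 50 (lower bound 21.2%). P(X ≥ 17 | 50, 0.40) = 0.844, as in Table 14.

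Both reproduce.

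**4. How far could local-only disease move the R/M ORR?** With local-only share w, pooled ORR = w × p_local + (1 − w) × p_distant, so it differs from p_distant by w × (p_local − p_distant). The documents give no w; 0.2 and 0.4 are assumed.

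- *Cited anti-PD-1 rates (Section 3.2.1):* 43.8% in LA disease and 47.5% in metastatic disease, a difference of −3.7 points. The shift is 0.2 × (−3.7) = −0.7 or 0.4 × (−3.7) = −1.5 points.
- *Planning values (Section 10.9.1):* the 30% is for the whole R/M cohort, so it is the pooled value. If local-only participants responded at the LA value of 40%, p_distant = (0.30 − 0.40w)/(1 − w). At w = 0.2 this is 0.22/0.8 = 27.5%. At w = 0.4 it is 0.14/0.6 = 23.3%. The pooled ORR would be 2.5 or 6.7 points above the distant rate.

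The two sources disagree on sign. The cited difference is itself imprecise: 43.8% is 7 of 16 (exact 95% CI 19.8% to 70.1%), and 47.5% of 59 has a CI of 34.3% to 60.9%. At 30 of 100 the exact interval is 21.2% to 40.0%, so its lower limit lies 30.0 − 21.2 = 8.8 points below the estimate. All four shifts are smaller than that.

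**5. What would a split show?** At a 30% response rate, 6 of 20 local-only participants gives 11.9% to 54.3%, and 12 of 40 gives 16.6% to 46.5%. Set against an LA result of 20 of 50 (26.4% to 54.8%), 12 of 40 differs by −10.0 points (Newcombe 95% CI −28.3 to 9.8).

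**The case for a change.** The best case for acting is that composition can matter more than these shifts suggest. Suppose the true distant-metastatic ORR were 20%, and 30 of 100 R/M participants had local disease responding at 40%. The pooled rate would be 0.3 × 40 + 0.7 × 20 = 26%. The probability that the lower bound exceeds 15% would rise from 26.1% (the Table 13 value at 20%) to 79.1%. At w = 0.5, a pooled 30% would imply a distant rate of (0.30 − 0.20)/0.5 = 20%, a 10-point gap that exceeds the 8.8 points above. The remedy also looks cheap: a few sentences in Section 6.1 and one line in Section 10.10, with stage at recurrence and sites of metastasis already collected under Section 9.1.4.1.

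The arithmetic stands, but the case for a change does not. The 20% and the local-only shares are assumptions, and the cited anti-PD-1 rates in metastatic disease are well above 20%. The 15% and 20% bounds are planning targets with no success rule attached. The example also concerns the mixture within R/M, which is the declared target population in Section 5.2, so an ORR for that mixture is what the plan sets out to estimate. Nor does a distant-versus-local split measure double eligibility: a local-only R/M participant may fail LA criterion 3 or 4, and the number of operations and radiotherapy ineligibility are not shown to be recorded for R/M participants.

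What survives is that Section 6.1 is looser than it should be, and that a clinical study report stating the cohort rule actually used would be easier to read.

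**Conclusion.** The entry criteria are not mutually exclusive as worded, and the documents name no cohort for an incurable, previously treated local recurrence that meets both sets. This is missing detail that analysts can fill sensibly: analyse each participant in the cohort recorded at allocation and describe disease extent at baseline. Each cohort's ORR then remains a valid estimate for the participants enrolled in it, with nobody counted twice. A rewritten Section 6.1 would not alter participants already allocated, and the extra subgroup would correct no stated number or conclusion.

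The direction and size of any effect on interpretation are unknown. In the illustrations with 20% or 40% local-only participants, the pooled R/M ORR lies between 1.5 points below and 6.7 points above the distant-metastatic rate, within the sampling error of a 100-participant cohort. A larger share with a large response difference could exceed that, but the documents give no evidence for either.

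The conclusion assumes that cohort is fixed at allocation, before response is known. The separate schedules and central allocation imply this, though no sentence says so. The supplemental SAP was not available and may already contain a disease-extent display.
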